# Observational Objective 1:

Antibody titers against meningococcal serogroup C measured by hSBA in each group:

- assessed before and at 30 days (+14 days) after vaccination
- $\geq 1:4$  and  $\geq 1:8$ , assessed at 30 days (+14 days) after vaccination
- post-vaccination / pre-vaccination titers ratio
- ≥4-fold rise from pre-vaccination to post-vaccination
- Vaccine seroresponse measured by hSBA, with seroresponse defined as:
  - for a subject with a pre-vaccination titer < 1:8, a post-vaccination titer  $\ge 1:16$
  - for a subject with a pre-vaccination titer ≥ 1:8, a post-vaccination titer at least 4-fold greater that the pre-vaccination titer.

# Observational Objective 2:

Antibody titers against meningococcal serogroup C measured by rSBA in each group:

- assessed before and at 30 days (+14 days) after vaccination
- $\geq 1.8$  and  $\geq 1.128$ , assessed before and at 30 days (+14 days) after vaccination
- post-vaccination / pre-vaccination titers ratio
- $\geq$ 4-fold rise from pre-vaccination to post-vaccination
- Vaccine seroresponse measured by rSBA, with seroresponse defined as:
  - for a subject with pre-vaccination titer < 1:8, a post-vaccination titer  $\ge 1:32$
  - for subjects with pre-vaccination titer ≥ 1:8, a post-vaccination titer at least 4-fold greater that the pre-vaccination titer.

# Safety

The following endpoints will be used for all subjects for the evaluation of safety:

- Unsolicited systemic AEs reported in the 30 minutes following the vaccination including occurrence, nature (Medical Dictionary for Regulatory Activities [MedDRA] preferred term), duration, intensity, relationship to vaccine and whether the AE led to early termination from the study.
- Solicited (pre-listed in the subject diary and the electronic CRF) injection site reactions and systemic reactions starting anytime from D0 (Day of vaccination) through D7 after the vaccination including: occurrence, time of onset, number of days of occurrence, intensity, action taken, and whether the reaction led to early termination from the study.
- Unsolicited non-serious AEs between D0 and D30 including: occurrence, nature, time of onset, duration, intensity, action taken, relationship to vaccine, whether the AE led to early termination from the study and outcome
- SAEs (including AESIs) throughout the study, i.e., from D0 to Visit 2 including: occurrence, nature, time of onset, duration, seriousness criterion, relationship to vaccine, whether the AE led to early termination from the study, outcome

See Section 9.3.2 of the protocol for more details.

# 4.4 Derived Endpoints: Calculation Methods

# **4.4.1** Safety

#### 4.4.1.1 Solicited Reactions

# 4.4.1.1.1 Daily Intensity

All daily records for solicited reactions will be derived into daily intensity according to the following classification: None, Grade 1, Grade 2, Grade 3, or Missing.

For the derivation of daily intensities, the following sequential steps will be applied:

- 1) Solicited reactions (except Fever) with an Investigator presence recorded as "No" and with all daily records missing then all daily intensities will be derived as None.
- 2) For a temperature partially missing after decimal point, the data will be analyzed replacing "MD" (missing data) by zero. For example, a "39.MD" daily temperature will be considered as "39.0°C" at the time of analysis.
- 3) For non-measurable solicited reactions, daily intensities will correspond to daily records reported in the clinical database. For measurable solicited reactions the daily measurements reported in the clinical database will be converted based upon the intensity scales defined in the protocol; this assumes a reaction that is too large to measure (non measurable, "NM") is Grade 3.

Note: The maximum intensity on the ongoing period is derived from the record of the maximum intensity/measurement after the end of the solicited period following the rule described above.

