#### **5.3.1** Amendment Justification

# **Amendment 1**

Due to the COVID-19 pandemic, subject enrollment was put on hold on 17 March 2020.

As this is a one-dose schedule, no ongoing participants were expected to receive further vaccination. The decision for each individual participant to remain in the study was to be made on a case by case basis based on the investigator's best medical judgement and the evolving situation at each site. Participants who could not be followed up as per protocol or could be followed up but out of the protocol defined window period, were to be kept in the study till the end of the study period and not automatically withdrawn from the study. Safety follow up could be accomplished via phone contact if an office or home visit was not possible.

These measures were taken by the Sponsor to ensure the well-being of subjects (ie, to limit exposure to COVID-19) and were implemented without IRB/EC approval, as per national and international guidance. However, IRB/EC and health authorities were informed promptly about the measures reported in the current amendment.

After ensuring subject safety, and with national health authority approval, enrollment will resume.

In the current amendment, the Sponsor will increase the sample size of the study to replace subjects excluded from the PPAS (see Section 12.5) to ensure the adequate power to fulfill the endpoints (see Section 9).

The study may be discontinued if new data about the investigational product resulting from this or any other studies become available; or for administrative reasons; or on advice of the Sponsor, the Investigators, the IECs/IRBs, or the governing regulatory authorities in the countries where the study is taking place.

If the study is prematurely terminated or suspended, the Sponsor shall promptly inform the Investigators, the IECs/IRBs, the regulatory authorities, and any contract research organization(s) used in the study of the reason for termination or suspension, as specified by applicable regulatory

requirements. The Investigator shall promptly inform the study subject's parents/legally acceptable representatives and should assure appropriate subject therapy and/or follow-up.

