# 13.2 Source Data and Source Documents

"Source data" are the data contained in source documents. Source documents are original documents or certified copies, and include, but are not limited to, diary cards, medical and hospital records, screening logs, informed consent form, telephone contact logs, and worksheets.

The purpose of study source documents is to document the existence of subjects and to substantiate the integrity of the study data collected. Investigators must maintain source documents so that they are accurate, complete, legible, and up to date.

For missing or discrepant data on a diary card, the study coordinator or designee will obtain verbal clarification from the subject, enter the response into the "Investigator's comment" page of the diary card, and transfer the information to the CRB.

The subject pre-screening log should list all individuals contacted by the Investigators to participate in the study, regardless of the outcome.

If electronic medical records are to be used, the Investigator must printa any Electronic Records on an ongoing basis, sign and date them immediately after creation, and keep the printouts on file as source documents that can be verified by the Sponsor or an inspector against the Electronic Records. Any subsequent changes of an electronic record require the record to be re-printed, dated (with an indication of the date of change), and signed. Such records must also be kept together with the original printed copy.

Good Documentation Practice should be followed by the Investigator and the site staff managing source documents.

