#### 4.4.1.1.3 Presence

Presence is derived from the maximum overall intensity on the period considered:

- None: No presence
- Grade 1, Grade 2, or Grade 3: Presence
- Missing: Missing presence

Subjects with at least one non-missing presence for a specific safety endpoint will be included in the analysis. Conversely, those without a non-missing presence will not be included in the analysis of the endpoint.

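### For solicited reactions other than fever, the SAP has no rule for an Investigator 'Yes' with no daily records, so a confirmed reaction would drop out of its endpoint

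*SAP*

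**What the plan says.** SAP 4.4.1.1.1 derives daily intensity in three sequential steps.

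- Step 1 opens "Solicited reactions (except Fever) with an Investigator presence recorded as" 'No' and sets every day to None when no daily record exists: "with an Investigator presence recorded as 'No' and with all daily records missing then all daily intensities will be derived as None".
- Step 2 concerns only temperatures with a missing decimal.
- Step 3 takes everything else from the daily data: "For non-measurable solicited reactions, daily intensities will correspond to daily records reported in the clinical database". Measurable reactions are graded from the daily measurements.

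SAP 4.4.1.1.3 then states: "Presence is derived from the maximum overall intensity on the period considered". Its last category reads "Missing: Missing presence", and "those without a non-missing presence will not be included in the analysis of the endpoint".

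No other section adds a rule. SAP 5.3.1.4 sends missing solicited intensities back to 4.4.1.1.1. SAP 5.3.1 and Protocol 12.3.1 both say that safety data are not replaced.

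**The concern.** Two children can have the same gap, a reaction with no daily record, and be treated differently according to the Investigator's answer. The 'No' child stays in the denominator without a reaction. The 'Yes' child disappears from that endpoint, although the Investigator has confirmed a reaction. If this pattern occurs, it can only lower the percentage.

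The protocol allows the pattern to arise. Protocol 9.3.2.1 makes the Investigator's assessment of solicited reactions mandatory. Protocol 13.2 provides for gaps: "For missing or discrepant data on a diary card, the study coordinator or designee will obtain verbal clarification". A parent may well remember that there was redness or irritability without being able to give a daily size or grade.

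The outcome also sits oddly with the SAP's other conventions, which keep uncertain events in. Missing causality counts as related (5.3.1.2), a reaction too large to measure is Grade 3 (4.4.1.1.1), and adverse events with missing onset stay in the tables (4.4.1.2.4, 4.4.1.3.3). For a confirmed solicited reaction without daily records, the SAP provides neither for counting nor for listing it.

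At stake is the description of reactogenicity for the three vaccines, which is an observational objective.

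**Working it through.** The plan states no solicited-reaction rate and no number of missing diaries, so there is no figure of its own to reproduce.

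**Tracing the rule for a child with no daily records (non-fever reaction)**

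| Investigator answer | Daily intensity | Presence | Numerator | Denominator |
|---|---|---|---|---|
| No | None (step 1) | No | 0 | 1 |
| Yes | Missing (step 3) | Missing | 0 | 0 |

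The rule applies to eight of the nine reactions in Protocol Tables 9.1 and 9.2. Fever is outside it: step 1 excludes fever, so neither answer is used.

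**Inputs**

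- N = 235 per group: the planned enrolment in SAP 5.5, assumed here to be the endpoint denominator.
- T, the children with the reaction: not in the documents. Assumed 24, 70 and 118, that is 10.2%, 29.8% and 50.2% of 235.
- k, the 'Yes' children with no daily records: not in the documents. Shown for 1, 5 and 10; zero is possible.

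**Formula**

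The full rate is T/N and the rate under the SAP is (T-k)/(N-k). The loss is

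T/N - (T-k)/(N-k) = k(N-T) / [N(N-k)],

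which is positive whenever k > 0 and T < N, and zero when k = 0.

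**Results** (SAP rate, with the change in percentage points)

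| T/N | k = 1 | k = 5 | k = 10 |
|---|---|---|---|
| 24/235 = 10.21% | 23/234 = 9.83% (-0.38) | 19/230 = 8.26% (-1.95) | 14/225 = 6.22% (-3.99) |
| 70/235 = 29.79% | 69/234 = 29.49% (-0.30) | 65/230 = 28.26% (-1.53) | 60/225 = 26.67% (-3.12) |
| 118/235 = 50.21% | 117/234 = 50.00% (-0.21) | 113/230 = 49.13% (-1.08) | 108/225 = 48.00% (-2.21) |

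The loss is about 0.2 to 0.4 points per such child. The columns for 5 and 10 show how it scales; they are not forecasts.

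**The case against.** The best defence is that step 1 may be a decoding rule. If the case report form leaves the daily fields blank once a reaction is marked 'No', blank fields after 'No' are normal data and None is their correct value. The fever exception fits, because temperature is recorded daily whether or not there is fever. A 'Yes' with blank fields would then be a data query. The form is not in the documents, so this reading can be neither confirmed nor excluded. It does not close the gap: the formula depends only on k, and the 'Yes' case has no rule under either reading.

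The protocol also works to keep k small. Parents are interviewed about incomplete entries (11.1), missing information must be explained (11.1), consistency checks look for omissions (11.2), and sites telephone for diaries that are not returned (5.1.4.3). This stands: k should be low.

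A reader might infer that the COVID-19 hold produced a sizeable group of such children, since Amendment 1 says "Safety follow up could be accomplished via phone contact if an office or home visit was not possible". The documents do not support that. The roughly 30 children were to be excluded from the per-protocol set because they could not complete the follow-up visit as planned. That visit falls 30 to 44 days after vaccination, whereas the Day 0 to Day 7 diary pages are filled in at home weeks earlier. A missed or late visit is not an empty diary.

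The analysis is also descriptive, with no safety test and the same rule in every group. That limits the consequence but does not justify discarding a confirmed reaction.

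**Conclusion.** The gap is in the text and its direction is certain: if any child has a 'Yes' with no daily records for a non-fever reaction, that reaction's reported rate is lower than the one obtained by counting the child. The size is about 0.2 to 0.4 percentage points per such child, assuming 235 children in the denominator and rates of 10% to 50%.

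It would go too far to say that the reported rates are biased downward. That requires k above zero, which the documents do not show. Nor do they show a distorted comparison between vaccines: the rule is common to all groups, so a distortion would need the number of such records or the underlying rates to differ between them. The child is lost only from that reaction's endpoint and remains in the safety analysis set. No hypothesis test is affected. This is a modest improvement, worth making because it is cheap.

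**What to change.** Add to SAP 4.4.1.1.1 and 4.4.1.1.3: for solicited reactions other than fever, Investigator presence 'Yes' with all daily records missing counts as presence = Yes with maximum intensity Missing. Show these children in their own row of the maximum-intensity table and report their number per group.

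This works under either form design and changes nothing if no such record exists. Setting both answers to Missing would also be symmetric, but it is not safe: if blank daily fields are the normal coding after 'No', it would remove true non-reactors from the denominator and inflate the rates.

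The cost is one SAP sentence and a small programming change before database lock. Some reaction percentages may become slightly higher, and a few reactions will have no grade.

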# 4.4.1.1.2 Maximum Overall Intensity

Maximum overall intensity is derived from the daily intensities computed as described in Section 4.4.1.1.1 and is calculated as the maximum of the daily intensities over the period considered.

#### 4.4.1.1.3 Presence

Presence is derived from the maximum overall intensity on the period considered:

- None: No presence
- Grade 1, Grade 2, or Grade 3: Presence
- Missing: Missing presence

Subjects with at least one non-missing presence for a specific safety endpoint will be included in the analysis. Conversely, those without a non-missing presence will not be included in the analysis of the endpoint.

#### **4.4.1.1.4** Time of Onset

Time of onset is derived from the daily intensities computed as described in Section 4.4.1.1.1. It corresponds to the first day with intensity of Grade 1, Grade 2, or Grade 3 during the solicited period (D0 to D07) after vaccination.

Note: If a reaction is not continuous (i.e., reaction occurs over two separate periods of time intervened by at least one daily intensity Missing or None) then the time of onset is the first day of the first occurrence during the solicited period (D0 to D07) after vaccination.

## 4.4.1.1.5 Number of Days of Occurrence

Number of days of occurrence over the over the solicited period (D0 to D07) is derived from the daily intensities computed as described in Section 4.4.1.1.1. It corresponds to the number of days with daily intensities of Grade 1, Grade 2, or Grade 3. Number of days of occurrence on the solicited period with a specified intensity may also be derived.

#### 4.4.1.1.6 Overall Number of Days of Occurrence

If a reaction is ongoing at the end of the solicited period, then the overall number of days of occurrence is derived from the daily intensities and the stop date of the reaction after the end of the solicited period. The overall number of days of occurrence is:

• (stop date – vaccination date) + (number of days of occurrence within the solicited period) – length of the solicited period + 1

If the stop date is missing or incomplete (contains MD), the overall number of days of occurrence will be considered as Missing.

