### 9.3.2.3.3 Unsolicited Adverse Events

In addition to recording solicited reactions, parent(s)/legally acceptable representative(s) will be instructed to record any other medical events that may occur during the 30 days (+ 14 days) period after vaccination. Space will be provided in the diary card for this purpose.

Information on SAEs will be collected and assessed throughout the study, from D0 to Visit 2 (ie, between D0 and D30 (+ 14 days)). Any SAE occurring at any time during the study will be reported by the Investigator in the CRB according to the completion instructions provided by the Sponsor; this includes checking the "Serious" box on the AE CRF and completing the appropriate Safety Complementary Information CRFs. All information concerning the SAE is to be reported either as part of the initial reporting or during follow-up reporting if relevant information became available later (eg, outcome, medical history, results of investigations, copy of hospitalization reports. In case a subject experiences febrile convulsion (neurological event associating fever and seizure), the assessment will be performed according to the "Guideline for definition and collection of cases of febrile convulsion", and this event will be considered an SAE. See Section 10 for further details on SAE reporting.

For each unsolicited AE (whether serious or non-serious), the following information is to be recorded:

- Start and stop datesa
- Intensity of the event:

For measurable unsolicited AEs that are part of the list of solicited reactions, the size of the AE as well as the temperature for fever will be collected and analyzed based on the corresponding scale used for solicited reactions (see Table 9.1 and Table 9.2).

All other unsolicited AEs will be classified according to the following intensity scale:

• Grade 1: A type of adverse event that is usually transient and may require only minimal treatment or therapeutic intervention. The event does not generally interfere with usual activities of daily living.

The stop date of all related AEs will be actively solicited. For other events, the investigator will provide the stop date when it becomes available. AEs for which no stop date was obtained during the course of the study will be considered as ongoing at the end of the study.

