#### 4.4.1.2.5 **Duration**

Duration is derived from the start and stop dates of the unsolicited non-serious AE provided in the clinical database:

• stop date of unsolicited non-serious AE - start date of unsolicited non-serious AE + 1.

The duration should be considered as missing only if one or both of the start and stop dates of the unsolicited non-serious AE is missing or partially missing.

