#### 4.4.1.3.4 **Duration**

Duration will be computed using the same methodology as for unsolicited non-serious AEs described in Section 4.4.1.2.5.

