# 5.3.1.5 Start Date and Stop Date

Missing or partially missing start dates for unsolicited AEs will remain missing and not be imputed. If either the start or stop date is missing or partially missing, the time of onset will be considered to be missing. Nevertheless unsolicited AEs with missing time of onset will be included in analyses according to the visit collected.

Missing or partially missing stop dates for AEs (solicited reactions and unsolicited AEs) will remain missing and not be imputed.

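### The SAP sets duration to missing for AEs and SAEs still ongoing at study end, so the descriptive duration summaries run short

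*SAP*

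**What the plan says.** - **Unsolicited non-serious AEs.** SAP 4.4.1.2.5 defines duration as stop date minus start date plus 1. It adds "The duration should be considered as missing only if one or both of the start and stop dates" are missing or partial.
- **SAEs, including AESIs.** SAP 4.4.1.3.4: "Duration will be computed using the same methodology as for unsolicited non-serious AEs".
- **Solicited reactions past D7.** SAP 4.4.1.1.6 uses the stop date to extend the count beyond D7 and rules: "If the stop date is missing or incomplete (contains MD), the overall number of days of occurrence will be considered as Missing". The separate D0 to D7 count in 4.4.1.1.5 uses daily intensities only.
- **No imputation.** SAP 5.3.1.5: "Missing or partially missing stop dates for AEs (solicited reactions and unsolicited AEs) will remain missing and not be imputed".
- **Status of events without a stop date.** The footnote in Protocol 9.3.2.3.3 says "AEs for which no stop date was obtained during the course of the study will be considered as ongoing at the end of the study". It also says "The stop date of all related AEs will be actively solicited"; for other events the investigator supplies the date if and when it is known.
- **Endpoints.** SAP 4.3 lists duration for immediate unsolicited AEs, unsolicited non-serious AEs and SAEs. For solicited reactions it lists number of days of occurrence.

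**The concern.** An event unresolved at the last contact lacks a stop date because it has not stopped. Its duration is right-censored: it lasted at least from onset to last contact. The SAP derives neither a minimum nor a censored value, so the event drops out of any summary of non-missing durations. The chance of dropping out rises with the true duration, so the missingness is informative and the remaining durations are too short on average.

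Duration is a listed safety endpoint, and describing the safety profile is a study objective. What is at stake is how long events appear to last, and whether a reader can tell an unresolved event from one with a poorly recorded date.

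**Working it through.** **1. The plan's own figure.** There is none. The documents give no rate of missing stop dates and no expected duration for unsolicited AEs.

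**2. One event followed through the rules (invented dates).** An unrelated, non-serious AE starts on D20 and is still present at Visit 2 on D35, and no stop date is ever supplied. Protocol status: ongoing. Known minimum, using the form of the 4.4.1.2.5 formula: 35 − 20 + 1 = 16 days. SAP duration: missing. A second AE running from D20 to D22 gives 22 − 20 + 1 = 3 days. The summary of non-missing durations over these two events is 3 days.

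**3. Direction and possible size, by simulation.** From the documents: unsolicited AEs are collected from D0 to D30, and Visit 2 falls on D30 to D44. Assumed: geometric durations, onset uniform over D0 to D30, Visit 2 uniform over D30 to D44, and no stop date obtained after Visit 2. Bias = complete-case mean / true mean − 1.

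| True mean (days) | Duration missing | Complete-case mean | Bias | Median, all vs complete-case | Share over 7 days, all vs complete-case |
|---|---|---|---|---|---|
| 3 | 1.3% | 2.93 | −2% | 2 vs 2 | 5.9% vs 5.3% |
| 7 | 8.2% | 6.01 | −14% | 5 vs 5 | 33.9% vs 29.0% |
| 14 | 23.6% | 9.00 | −36% | 10 vs 7 | 59.6% vs 47.9% |

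**4. Solicited-type events.** With onset assumed uniform over D0 to D3, 0.0%, 0.5% and 7.1% are missing, with bias of about 0%, −2% and −19%. Protocol 1.2.1.2 reports that most solicited reactions in the earlier Phase III toddler study lasted 1 to 3 days; at that length the bias is about zero.

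**5. Partial stop dates.** If 5% of durations are lost for reasons unrelated to length, a true mean of 7.00 stays at 7.00. Loss of that kind costs precision but causes no bias.

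**6. What keeping the censored events would recover.** In the step 3 setting, counting each unresolved event up to Visit 2 gives means of 2.96, 6.43 and 10.70. A Kaplan-Meier mean restricted to 44 days gives 3.00, 6.99 and 13.48. Minimum durations therefore remove only part of the bias.

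**The case against.** The strongest reply is that the two documents do not conflict. The protocol footnote assigns a status and prescribes no duration, so an ongoing event with an undefined duration is consistent with it. That stands: this is a weakness in the derivation, and the documents do not support reading it as a contradiction between protocol and SAP.

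Second, follow-up limits the loss. Solicited reactions are related by definition (Protocol 9.3.2.1), and stop dates of related AEs are actively sought. Protocol 5.1.4.3 and 9.3.2.3.5 extend follow-up of related AEs beyond the end of participation, and 5.1.4.3 does the same for AEs that led to discontinuation. Protocol 10 and 10.2 require SAE documentation and updates regardless of causality. This stands in large part. It leaves unrelated non-serious AEs, and events whose follow-up ends because they are stable or chronic and so have no stop date to collect.

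Third, outcome is summarized as collected (SAP 4.4.1.4.4) and listings mark missing data (SAP 5.3.1). This helps a careful reader but does not correct the duration summary. SAP Table 5.1, which sets out the descriptive statistics, is not in the text available to us, so a row for missing durations may exist. Such a row would still mix ongoing events with incomplete dates.

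Fourth, Protocol 12.3.1 and SAP 5.3.1 rule out replacement of safety data. That is a fair argument against entering the last contact as a stop date or completing partial dates. It does not bar an ongoing category.

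**Conclusion.** The point holds for unsolicited AEs and SAEs with no stop date at all: summaries of non-missing durations are biased downward. The direction rests on the protocol's convention that an absent stop date means an ongoing event. The size cannot be taken from the documents; the −2% to −36% above depends on assumed durations and on no stop date being obtained after Visit 2. Safety is descriptive here, so no test, margin or sample size is affected. This is a low-cost improvement.

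A reader might infer three stronger things that the documents do not support:

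- **That a solicited reaction unresolved at Visit 2 contributes nothing to the listed endpoint.** It still contributes its D0 to D7 days under SAP 4.4.1.1.5. Section 4.4.1.1.6 concerns only the additional overall count, and only for reactions that SAP 4.4.1.1.7 classes as ongoing.
- **That every incomplete stop date biases the result.** A partial date shows that an end was recorded; the protocol does not call that event ongoing, and its loss need not depend on duration.
- **That every dropped event is a long one.** An AE starting on D28 and unresolved at a D30 visit is known only to have lasted at least 3 days. Dropped events tend to be longer, but this is not true of each one.

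**What to change.** In SAP 4.4.1.2.5 and 4.4.1.3.4, when the stop date is entirely absent:

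- classify the event as ongoing at end of study;
- show it in its own row, within the denominator of the duration table;
- list its minimum duration, flagged as a minimum: the later of last visit and termination date, minus start date, plus 1.

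Do not impute a stop date. Keep durations with a partial stop date as missing, reported separately from ongoing events. For consistency, add the same ongoing row to the overall number of days in 4.4.1.1.6. Leave the D0 to D7 count in 4.4.1.1.5 unchanged.

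The cost is a sentence or two per section, one derivation and one table row. No new data are needed: SAP 4.4.3.2 already uses the last-visit and termination dates. The limitation is that minimum durations still understate the true ones, so they should be listed as minima and not averaged with complete durations.
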